### **3.4.2.2 Duration of Response**

Duration of response (DoR) is defined as the time from the first documentation of a subsequently confirmed OR until the first documentation of a disease progression or death due to any cause, whichever occurs first, regardless of whether the subject receives subsequent anticancer treatment prior to progression. Only subjects who have achieved OR (confirmed CR or confirmed PR) will be evaluated for DoR. DoR is defined in months as follows:

$$\text{DoR (months)} = (\text{Date of PD/death or censoring} - \text{Date of first confirmed disease response} + 1) / (365.25/12)$$

The date of PD/death or censoring is the same as defined for PFS in Section 3.4.2.4. The median DoR and its 95% CI will be estimated using the Kaplan-Meier method.

### **3.4.2.3 Disease Control**

Disease control rate (DCR) is defined as the proportion of subjects with a BOR of confirmed CR, confirmed PR, or SD (maintained for  $\geq 16$  weeks). DCR will be estimated with a 95% CI using the exact probability method. An estimate of the difference in DCR between each experimental arm and control arm will be reported and tested for significance with the Cochran–Mantel–Haenszel test.

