| Serum chemistry                     | X                    | X d                                     | X                        | X                        | X                        | X  |
| Hematology                          | X                    | X d                                     | X                        | X                        | X                        | X  |
| Urinalysis                          | X                    | As clinically indicated                            |                          |                          |                          |  |
| Thyroid function tests e | X                    | X d                                     | X                        | X                        | X                        | X  |
| Pregnancy test f         | X                    | X  | X                        | X                        | X                        | X  |
| Coagulation parameters              | X                    |  |                          |                          |                          |  |
| Hepatitis B and C; HIV g | X                    |  |                          |                          |                          |  |
| Concomitant medications             | X                    | X  | X                        | X                        | X                        | X  |
| Assessment of AEs/SAEs              | X                    | X  | X                        | X                        | X                        | X  |
| Disease assessment (scans)          | X h       |  |                          | X
(within 7 days)     |                          | Cycle 5 then every 2 cycles
(within 7 days) |

**Table 5** Schedule of Screening and Treatment Period Procedures

| Procedure                              | Screening         | Treatment Period: Up to 12 Months
28-day Cycles |                          |                          |                          |   |
|--|-------------------|--|--------------------------|--------------------------|--------------------------|---|
|  |                   | Cycle 1  | Cycle 2                  | Cycle 3                  | Cycle 4                  | Cycle 5 through Cycle 13                            |

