### **4.6 Treatment Assignment and Blinding**

#### **4.6.1 Methods for Assigning Treatment Groups**

Once confirmed that the subject meets eligibility criteria, an IXRS will randomize the subject to a treatment arm according to the randomization scheme.

A randomization method with dynamically changing randomization ratios will be employed to account for fluctuation in the number of treatment arms open for enrollment over the course of the study. Randomization will be stratified by histology (adenocarcinoma vs non-adenocarcinoma). The randomization scheme will use an equal ratio to all study treatment arms open for enrollment (eg, if experimental arms are opened sequentially, an experimental arm is added/closed, or enrollment in an experimental arm is suspended). Additionally, the following considerations regarding randomization will apply:

- If there is no experimental arm open for enrollment, then enrollment will be paused. Any subject who had consented previously and was in screening when the experimental arm(s) was closed due to safety concerns may be allowed to enter into the study but must be allocated to the control arm.
- Once the control arm enrolls 60 subjects, a subsequent randomization scheme may be initiated to optimize the number of subjects allocated to control arm.
- At any point during the study, the control arm will have no less than a 33% chance to be randomized in comparison to the active experimental arm that has the lowest randomization ratio in the study.

Study treatment must be administered within 3 days after the treatment arm is assigned. If there is a delay in the administration of study treatment such that it will not be administered within the specified timeframe, the study monitor must be notified immediately.

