#### 4.8.3      Efficacy

The final efficacy analyses will be based on the ITT Population defined in Section 4.8.1. Response will be summarized and compared between the experimental arm and control arm. Time-to-event data will be summarized using the Kaplan-Meier estimates. The following efficacy endpoints will be analyzed. Each experimental arm will be compared to the control arm. There will be no formal comparisons between any experimental arms. RECIST v1.1 will be used as primary analysis for all endpoints when applicable. Localized post-radiation changes which affect lesion sizes may occur and there may be high levels of necrosis/fibrosis with little or no active tumor in recently irradiated lesions. However, accepting these limitations in this patient population with prior curative radiation, treatment the prior irradiated lesions may be considered measurable and selected as target lesions providing they fulfill the other criteria for measurability. More details will be provided in the statistical analysis plan.

- Best overall response (BOR), defined as the best response (in the order of complete response [CR], PR, SD, PD, and not evaluable) among all overall responses recorded from randomization until progression, or the last evaluable disease assessment in the absence of PD prior to the initiation of subsequent anticancer therapy or discontinuation from the study, whichever occurs first. The BOR of CR or PR must be confirmed, which means a response of CR/PR is recorded at 1 visit and confirmed by repeat imaging not less than 28 days (4 weeks) after the visit when the response was first observed with no evidence of progression between the initial and CR/PR confirmation visit.
- OR, defined as BOR of confirmed CR or confirmed PR according to RECIST v1.1.
- DC, defined as BOR of confirmed CR, confirmed PR, or SD based on RECIST v1.1. Disease control rate (DCR) at 16 weeks is defined as a BOR of confirmed CR, confirmed PR or having SD with duration of SD lasting 16 weeks.
- DoR, defined as the time from the first documentation of a subsequently confirmed OR to the first documentation of a disease progression according to RECIST v1.1 or death due to any cause, whichever occurs first. Only subjects who have achieved OR (confirmed CR or confirmed PR) will be evaluated for DoR.

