#### **3.4.2.1 Best Overall Response**

Best overall response (BOR) will be based on all post-baseline disease assessments that occur prior to disease progression, and/or prior to the initiation of subsequent anticancer treatment. BOR will be summarized with the number and percentage of subjects for the following categories: complete response (CR); partial response (PR); stable disease (SD); progressive disease (PD); and non-evaluable (NE). At least 7 weeks (8 weeks minus 1 week to allow for the protocol-defined disease assessment window) from randomization of IP must elapse without a subsequently radiological disease progression to assign a best overall response of SD.

Confirmation of CR and PR is required and must occur at least 4 weeks after initial documentation of CR or PR. If CR is pending confirmation and is designated at an assessment followed by 1 or more NE assessments, and/or PR assessments such that 1) the Target Lesion Response is CR and the Non-Target Lesion Response is NE, or 2) the Target Lesion Response is PR due solely to an increase in one or more lymph nodes to a size  $\geq 10$  mm and the Non-Target Lesion Response is either CR or NE, CR may be confirmed thereafter. Similarly, if a PR is pending confirmation and is designated at an assessment followed by 1 or more NE and/or SD assessments, PR may be confirmed thereafter.

In general, subjects not classifiable under the RECIST v1.1 response categories due to insufficient data or early death will be classified as NE for BOR but will be counted in the denominator of all response rate calculations. This generalization includes if a subject has missing lesion data at baseline. In this scenario, the subject will be classified as NE for BOR.

If a subject is missing lesion data at a disease assessment and yet PD criteria is met despite the missing data, the subject will be classified as PD.

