**Table 3.4.1      Summary of Censoring Guidelines for PFS**

Situation	Date of PD/Death or Censoring	PFS Outcome
Documented Progressive Disease (PD) or death	Date of earliest sign of PD or death, whichever comes first	Event (unless the censoring rule specified below)
Death or PD immediately after $\geq 2$ consecutive missed or non-evaluable disease assessments as per the protocol specified assessment schedule	Date of last progression-free disease assessment prior to missed or non-evaluable assessments, or randomization, whichever occurred last	Censored
No PD or death at time of analysis or lost to follow-up	Date of last evaluable progression-free disease assessment	Censored
No tumor assessment at baseline and no evidence of PD at first post-baseline disease assessment OR No tumor assessment post-first dose, and no death prior to second scheduled post-baseline disease assessment	Date of randomization	Censored

PD = progressive disease; PFS = progression-free survival.

Subjects having missing lesion data at baseline or no disease assessments post-first dose of IP will have PFS censored at the date of randomization unless the subject dies prior to the second scheduled post-baseline disease assessment in which case the death date will qualify as a PFS event.

If a subject has two or more consecutive completely missed or non-evaluable assessments followed immediately by death or an assessment showing radiologic disease progression, then the subject will be censored for PFS. PFS will be censored at the date of randomization or the last progression-free disease assessment prior to the missed or non-evaluable assessments, whichever occurred last.

If a subject has two or more consecutively missed or non-evaluable assessments followed by an assessment showing no radiologic disease progression, then the assumption will be that the subject did not progress during the missed or non-evaluable assessments.

The length of gap (in number of days) to determine two or more consecutive assessments is defined as the following:

- 126 days during the first 12 months (A 8-week disease assessment interval plus a 7-day window for each assessment).

- 182 days from month 12 to month 24 (A 12-week disease assessment interval plus a 7-day window for each assessment).
- 422 days after month 24 (A 6-month disease assessment interval plus a 4-week window for each assessment).

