## 4 INTERIM ANALYSIS

Interim analyses comparing durvalumab in combination with novel agents to durvalumab alone will be performed in a continuous manner using a joint Bayesian predictive probability. Bayesian predictive probability has been used in the setting of single-arm trials with tumor response endpoints such as OR and allows for continuous assessments for early Go/No-Go decision making ([Lee and Liu, 2008](#)). A joint Bayesian predictive probability approach

allows for continuous assessments of the delta ( $\Delta$ ), or difference, of the DCRs between durvalumab/novel agent combinations and durvalumab alone ([Pulkstenis et al., 2017](#)).

Interim analyses will begin after approximately 30 subjects in control arm (durvalumab alone) have been randomized and have reached the data cutoff criterion. The data cutoff criterion is defined as the opportunity to be followed for at least 16 weeks at the time of the data cutoff (i.e., dosed at least 16 weeks prior to the time of the data cutoff). The interim analysis will be based on the subset of the ITT Population that have satisfied the data cutoff criteria. Enrollment will not pause during the interim analysis before the decision is made.

Following this initial interim analysis, subsequent interim analyses will be performed for each experimental arm regardless of whether it starts enrollment later than control arm. Specifically, an interim analysis will be performed once each experimental arm has approximately 30 ITT subjects reach the data cutoff criterion. For interim analyses that will lead to an early No-Go decision, a response is defined as either a confirmed or unconfirmed CR or PR as per RECIST v1.1. Only concurrent control subjects, i.e., enrolled during the same period as the experimental arm, will be included in interim analyses. A comparison of each experimental arm versus all control subjects may be included as a supportive analysis.

The Target Value (TV) is set to demonstrate a 15% increase in  $\Delta$ DCR at 16 weeks, where  $\Delta$ DCR is the difference in DCR between an experimental arm and control arm. At final analysis, No-Go criteria will be met if the probability that the true  $\Delta$ DCR exceeds the prespecified TV of 15% is less than 10% (i.e., No-Go:  $P[\Delta\text{DCR} > \text{TV}] < 10\%$ ).

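### Disease control at 16 weeks has no scan-window allowance and no stated way to measure SD duration, so an early but on-time Cycle 5 scan may not count

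*SAP*

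**What the plan says.** SAP 3.4.2.3: "Disease control rate (DCR) is defined as the proportion of subjects with a BOR of confirmed CR, confirmed PR, or SD (maintained for" at least 16 weeks). Protocol 4.8.3 words the SD part of DCR at 16 weeks as "having SD with duration of SD lasting 16 weeks". Neither mentions a scan window, and neither says on what date SD duration ends.

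SAP 3.4.2.1 does allow for the window when it assigns a best response of SD: "At least 7 weeks (8 weeks minus 1 week to allow for the protocol-defined disease assessment window) from randomization". The missed-assessment rule under SAP Table 3.4.1 also uses one: "A 8-week disease assessment interval plus a 7-day window for each assessment".

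Protocol Table 5 has 28-day cycles and schedules scans at Cycle 3 and then "Cycle 5 then every 2 cycles", within 7 days. Protocol 4.6.1 sets the dosing lag: "Study treatment must be administered within 3 days after the treatment arm is assigned".

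SAP Section 4 admits a subject to the interim if "dosed at least 16 weeks prior to the time of the data cutoff". Protocol 4.8.7 asks only for the opportunity of 16 weeks' follow-up and does not tie it to dosing. DCR at 16 weeks drives the No-Go decision, and for that decision unconfirmed CR and PR count as response.

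**The concern.** The scan that should establish 16 weeks of SD is scheduled on the threshold itself. A scan done a few days early, but inside its window, documents less than 16 weeks. A scan done a few days late may not yet exist for a subject who has only just met the 16-week cutoff. The SAP removes this problem at 8 weeks by taking off one week, but not at 16 weeks.

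At stake is misclassification in the endpoint that can close an arm, and, to a small extent, in the reported DCR. A smaller matter is that a cutoff counted from dosing can never be met by a randomised subject who was not dosed, although the interim set is drawn from the ITT Population.

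**Working it through.** **1. The plan's own figures.** SAP Section 4 states no prior. I used independent Beta(1,1) priors and exact enumeration. Final No-Go: P(ΔDCR > 0.15) < 0.10 at 60 per arm. Early No-Go: predictive probability of that result > 0.95 at 30 per arm. Control DCR is 60%.

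| True difference (points) | 0 | 5 | 10 | 15 | 20 | 25 |
|---|---|---|---|---|---|---|
| All No-Go, Table 4.2 (%) | 68 | 46 | 25 | 11 | 3 | 1 |
| All No-Go, computed (%) | 68.4 | 46.9 | 25.9 | 11.0 | 3.5 | 0.7 |
| Early No-Go, Table 4.2 (%) | 19 | 11 | 5 | 2 | 1 | 0 |
| Early No-Go, computed (%) | 19.0 | 10.5 | 5.1 | 2.1 | 0.7 | 0.2 |

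The cut-offs match 20 of the 21 rows of Table 4.1. With 28 controls the table gives ≤28 and I get ≤27. The model is close enough to use.

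**2. Day count, if SD ends at the last SD scan.** Cycle 5 Day 1 is 4 × 28 = 112 days after first dose. Let the scan fall on day 112 + w, with w from −7 to +7 (15 days, taken as equally likely), and let dosing follow randomisation by L = 0 to 3 days. The time from randomisation is 112 + w + L, which is short of 112 when w + L < 0.

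- Share short = (7 − L)/15: 7/15 = 47% at L = 0 and 4/15 = 27% at L = 3. The mean over L = 0 to 3 is (7+6+5+4)/60 = 37%.
- With the +1-day convention of the SAP's time formulas: (6 − L)/15, so 40% down to 20%.
- If "within 7 days" means before only: (7 − L)/8, so 88% down to 50%. If it means after only: 0%.

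**3. Who is affected at the interim.** The next scan is at Cycle 7, 6 × 28 = 168 days or 24 weeks after first dose. A shortfall therefore stays unrepaired mainly in subjects 16 to 24 weeks from dosing. With uniform accrual over A weeks (assumed) that is 8/A of the interim set. In addition, the 1/A of subjects at 16 to 17 weeks may have an on-time scan still to come. A subject f days past day 112 has (7 − f)/15 of scan days ahead, which averages 28/(7 × 15) = 0.267 over f = 0 to 6.

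Missed share of SD subjects ≈ 0.367 × 8/A + 0.267/A.

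**4. Effect on DCR.** Table 4.2 takes control DCR as 60% and Table 7.2-2 takes control ORR as 30%. Treating the difference, 30 points, as SD is my assumption. Loss = 30 × missed share.

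| Accrual (weeks) | 8 | 16 | 24 | 36 |
|---|---|---|---|---|
| Missed share of SD | 40% | 20% | 13% | 9% |
| DCR lowered by (points) | 12.0 | 6.0 | 4.0 | 2.7 |

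**5. Effect on early No-Go at a true difference of 15 points,** with the same missed share in both arms:

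| Missed share of SD | 0 | 10% | 20% | 40% | 47% |
|---|---|---|---|---|---|
| Gain all in SD (%) | 2.1 | 2.7 | 3.4 | 5.5 | 6.4 |
| Gain proportional (%) | 2.1 | 2.4 | 2.6 | 3.3 | 3.6 |
| Gain all in response (%) | 2.1 | 2.0 | 2.0 | 1.9 | 1.9 |

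The mechanism at 20% missed: control shows 30 + 0.8 × 30 = 54%. The experimental arm shows 30 + 0.8 × 45 = 66% if the gain is all SD (difference 12), or 45 + 0.8 × 30 = 69% if it is all response (difference still 15). At a true difference of zero, early No-Go moves only from 19.0% to about 18.4%.

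**6. After the change.** The earliest on-time scan is 112 − 7 + 0 = 105 days from randomisation, exactly 15 weeks, so no on-time scan falls short. The latest is 112 + 7 + 3 = 122 days.

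**The case against.** The strongest objection is that the SAP never says SD duration stops at the last SD scan. SAP 3.4.2.1 speaks of time elapsing without progression. Read that way, SD seen on day 108 with no progression satisfies 16 weeks once day 112 has passed, as it has for every interim subject. This stands as an ambiguity, and a reader who infers that many on-time SD subjects do count as failures goes further than the text. Scan-based counting is still the likelier reading. The week taken off in 3.4.2.1 is explained by the scan window, SAP 3.4.2.4 censors PFS at the last evaluable assessment, and SAP 7.1.5 uses the SD assessment date for censoring. The other reading has its own fault: a subject whose Cycle 5 scan is pending could be credited with 16 weeks on a Cycle 3 scan.

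It is also fair that both arms lose subjects, that responders (including unconfirmed ones) are untouched, and that Cycle 7 scans repair most cases. So one cannot infer a general bias against the experimental arms. Nor can one infer that DCR is pushed away from the 60% benchmark: the SAP does not say how that figure was derived, and it may already reflect the 16-week rule. The SAP openly calls the interim set a subset of ITT, and the number of undosed subjects is unknown.

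Finally, Protocol 9.1 records that all subjects have completed treatment, and the SAP version history refers to a reviewed first interim. For the present arms the stopping rule has little left to decide.

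**Conclusion.** The concern holds in limited form. The 16-week SD rule lacks the allowance that the SAP gives its 8-week rule, SD duration is undefined, and the interim cutoff can precede an on-time scan on days 113 to 119. On the likely reading, 27% to 47% of on-time Cycle 5 scans are too early to count. At the interim this costs about 3 to 6 points of DCR for accrual over 16 to 36 weeks and more for faster accrual. It is confined to SD subjects with short follow-up, in both arms. Early No-Go at a true difference of 15 points goes from about 2% to somewhere between 2% and 6%. The upper end needs the whole gain in SD, no dosing lag, and all interim subjects accrued within 8 weeks.

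The final DCR is little affected. What remains there is an arbitrary split: for a subject dosed on the day of randomisation, SD on day 108 followed by PD at Cycle 7 fails, whereas SD on day 113 followed by PD passes.

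These sizes rest on assumptions that are not in the documents: the Beta(1,1) prior, uniform scan days over ±7 days of the nominal date, uniform accrual, and 30 points of SD. The ORR benchmark behind that last figure belongs to the Go rule, which uses confirmed response. Counting unconfirmed responses, as the No-Go does, would leave fewer SD subjects exposed.

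**What to change.** - **SAP 3.4.2.3:** state that SD duration runs from randomisation to the last progression-free assessment, and count SD of at least 15 weeks (16 weeks minus the 7-day window) as disease control at 16 weeks.
- **SAP Section 4:** set the interim criterion at randomised at least 122 days before the cutoff (17 weeks plus the 3-day dosing lag). Seventeen weeks from randomisation alone, 119 days, would not close the window for a subject dosed three days later. Counting from randomisation also keeps undosed subjects in the ITT-based set.
- **Reporting:** state how SD duration was derived at the interims already held. Because those data have been seen, show the final DCR under the 16-week wording next to the 15-week rule.

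The cost is two SAP sentences and an interim cutoff about 10 days later (122 − 112). No new data are needed.

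### Disease control needs 16 weeks of SD with no scan-window allowance and no dating rule, so for subjects with SD the permitted scan date alone can decide the endpoint; the direction of the effect on the DCR difference is not fixed

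*SAP*

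**What the plan says.** The definition in SAP 3.4.2.3 reads: "Disease control rate (DCR) is defined as the proportion of subjects with a BOR of confirmed CR, confirmed PR, or SD (maintained for"; the duration then given is 16 weeks or longer. Protocol 4.8.3 defines DCR at 16 weeks as confirmed CR, confirmed PR, or "having SD with duration of SD lasting 16 weeks". Neither text mentions a scan window, a start and stop date for SD, or a required scan.

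Elsewhere the SAP does allow for the window. For a best overall response of SD, SAP 3.4.2.1 asks for "At least 7 weeks (8 weeks minus 1 week to allow for the protocol-defined disease assessment window) from randomization" without radiological progression. The rule for missed assessments under SAP Table 3.4.1 explains its first-year gap as "A 8-week disease assessment interval plus a 7-day window for each assessment", which gives 2 × (56 + 7) = 126 days.

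The timing comes from the protocol. Table 5 schedules scans at Cycle 3, then "Cycle 5 then every 2 cycles", within 7 days, in 28-day cycles. Section 4.6.1 adds: "Study treatment must be administered within 3 days after the treatment arm is assigned".

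DCR at 16 weeks is the No-Go measure (protocol 4.8.7, SAP Section 4) and is tested between arms (SAP 3.4.2.3). The interim data cutoff criterion is "dosed at least 16 weeks prior to the time of the data cutoff", again without a window.

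**The concern.** The scan that shows whether SD reached 16 weeks is the one whose permitted dates straddle 16 weeks. Two subjects with the same findings can then differ on the endpoint because of the day they were scanned. Which subjects are affected depends on a dating rule that the SAP does not give:

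- **SD dated to the last SD scan.** SD on an on-schedule scan at day 108, with no later non-PD scan, is a failure. The same finding at day 113 is a success.
- **SD dated to PD.** SD at week 8 and PD first seen on an on-schedule scan at day 115 counts as 16 weeks of control. The same PD at day 110 does not.

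At an interim, the cutoff of 112 days from dosing also means that a subject whose in-window scan falls later may have only the week-8 scan.

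At stake are the observed DCR, the DCR difference behind No-Go, and whether two programmers would derive the same value.

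**Working it through.** **1. Scan dates.** Cycle 5 Day 1 is 4 × 28 = 112 days after first dose. With ±7 days and a lag of 0 to 3 days from randomization to dosing, there are 15 × 4 = 60 combinations, assumed equally likely. Of these, 22 fall before day 112 from randomization (37%) and 38 on or after it (63%). Other assumptions give other shares:

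- The SAP's convention of adding one day puts 30% before day 112.
- Scans kept within ±3 days put 11–21% before it.
- Scans taken only in the 7 days up to the visit leave about a third (31–33%) on or after it. Table 5 prints no ± for scans.

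**2. The plan's own figures.** The SAP states no prior, so Beta(1,1) is assumed in each arm. There is one look at 30 per arm and a final analysis at 60 per arm. No-Go is P(ΔDCR > 15%) < 10%, and early No-Go is predictive probability > 95%. Exact enumeration at control DCR 60%:

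| True Δ | 0% | 5% | 10% | 15% | 20% | 25% |
|---|---|---|---|---|---|---|
| SAP Table 4.2, all No-Go | 68 | 46 | 25 | 11 | 3 | 1 |
| Recomputed, all No-Go | 68.4 | 46.9 | 25.9 | 11.0 | 3.5 | 0.7 |
| SAP Table 4.2, early | 19 | 11 | 5 | 2 | 1 | 0 |
| Recomputed, early | 19.0 | 10.5 | 5.1 | 2.1 | 0.7 | 0.2 |

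All are within one point. SAP Table 4.1 is reproduced in 20 of 21 rows (for 28 controls, 27 computed against 28 printed).

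**3. SD dated to PD.** Let p be the proportion free of PD at the week-16 scan and f the share of those scans on or after day 112. With exponential progression, the proportion free of PD at week 8 is √p, so √p − p first show PD at week 16. A fraction f of these counts as controlled:

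observed DCR = p + f(√p − p)

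- Control, p = 0.60, f = 0.633: 0.60 + 0.633 × 0.175 = 0.711
- Experimental, p = 0.75: 0.75 + 0.633 × 0.116 = 0.823
- Difference: 11.3 points instead of 15
- All No-Go 24% (25% with rates rounded to 71% and 82%), early No-Go 5%

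With f = 0.333 (scans only before the visit), the rates are 65.8% and 78.9%, the difference is 13 points, all No-Go is 17% and early No-Go 3.4%.

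**4. SD dated to the last SD scan.** Suppose a fraction L of SD subjects is lost, equally in both arms. With s the rate of SD lasting 16 weeks:

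observed Δ = true Δ − L × (s_exp − s_ctl)

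The control split is 30% response (SAP Table 7.2-2 benchmark) plus 60 − 30 = 30% SD. With L = 22/60 = 36.7% and true Δ = 15 points:

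| Experimental arm (response + SD) | Observed Δ | All No-Go | Early |
|---|---|---|---|
| 30 + 45, gain all SD | 15 − 0.367 × 15 = 9.5 | 28% | 5.0% |
| 37.5 + 37.5, half each | 15 − 0.367 × 7.5 = 12.3 | 19% | 3.2% |
| 45 + 30, gain all response | 15.0 | 12% | 1.9% |
| 50 + 25 | 15 + 0.367 × 5 = 16.8 | 8% | 1.3% |

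This L is an upper bound, because a later non-PD scan restores the subject. The all-No-Go column also requires the loss to persist to the final analysis.

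**5. With a one-week allowance.** The threshold becomes 105 days. None of the 60 combinations falls short, and the figures in SAP Table 4.2 stand.

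**The case against.** A reader might infer that the missing window shrinks the DCR difference and so makes the trial more likely to drop an effective arm. The documents do not support that as a general statement. It follows from dating SD to PD, which the SAP does not specify. Under the other dating, the difference can hold or grow, and the trial's primary endpoint is response, not SD.

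Further points against the concern, and what stands of each:

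- The SAP dates progression to the scan that shows it, so PD first seen at day 115 also gives PFS beyond 16 weeks. Counting that subject as controlled agrees with PFS and is not plainly wrong. This stands. It does not explain why the same finding at day 110 should count differently, or why SD at week 8 gets a window and SD at week 16 does not.
- The 60% benchmark may already refer to DCR as the plan defines it. If so, Table 4.2 stands at 11% and 2%. Nothing in the documents settles this, so step 3 is illustrative.
- Deaths, and progression found at unscheduled assessments, do not follow the scan window. Confirmed responders are untouched, as are unconfirmed ones at No-Go interims. All of this reduces the effect.
- The SAP version history refers to a completed first interim, and protocol Amendment 4 says that all subjects have finished treatment. The cutoff therefore matters only for any further interim. The DCR definition still matters for the final report.

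**Conclusion.** The omission is real, and the SAP is inconsistent with itself: the 7-day window is allowed for SD at week 8 and in the PFS gap rule, but not for SD at week 16. For subjects whose disease control rests on SD, a permitted scan date can decide the endpoint under either reading.

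The size is uncertain. Under time-to-PD dating, with exponential progression, uniform ±7-day scans and a benchmark that means the week-16 scan result, 15 points become about 11. Total No-Go goes from 11% to about 24–25%, and early No-Go from 2% to about 5%. It is 13 points and 17% if scans only precede the visit. Under last-SD-scan dating, the observed difference runs from about 9.5 to 16.8 points across the splits tried, as an upper bound on the loss.

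Early No-Go, the decision that stops enrollment, moves by only about three points even in the worse cases shown. This should be corrected, but it does not show that any No-Go decision was or would be wrong.

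**What to change.** - **SAP 3.4.2.3 and protocol 4.8.3:** define the SD component as an evaluable SD-or-better assessment at least 15 weeks (105 days) after randomization, with no PD at or before that assessment. This is 16 weeks minus the one-week window, the convention already used in SAP 3.4.2.1, and it removes the need to date SD duration.
- **SAP Section 4:** apply the same SD rule, but keep its rule that confirmed or unconfirmed CR/PR counts at No-Go interims.
- **Any further interim only:** set the cutoff at 16 weeks plus the scan window, 17 weeks from dosing, so that an on-schedule scan can be present.
- **Scan window:** state whether the 7 days run from the nominal or the actual visit. If they add to the ±3-day visit window, the earliest scan is day 112 − 3 − 7 = 102 after dosing, and a few permitted scans would still miss 105 days.

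The cost is a short SAP change and one derivation line. The reported DCR may change slightly. Because interim data in this open-label trial have been seen, the change and its reason should be documented, and DCR under the present wording, with the dating used stated, should be shown as a sensitivity analysis.
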